Using procedures and assessments already approved, collateral informants will be interviewed to corroborate self-reports of drinking. All participants will complete two collateral letter forms at the intake session with the option to opt out completely or to only provide one collateral informant. If a visit is not scheduled after a minimum of three attempts using the participant's preferred mode of contact, or if a visit is not scheduled by the remaining two weeks of their visit window, collateral letters will be either mailed or emailed to informants depending on the contact information provided by the participant. These letters inform the collateral that the subject is participating in this study and that he has given the study personnel permission to call them should there be a loss of contact with the participant. These letters also note that the participant has given us permission to ask them questions regarding the participant's drinking. If a follow-up visit is not scheduled after a minimum of three attempts using the participant's preferred mode of contact, or if a visit is not scheduled after a minimum of three attempts using the participant's preferred mode of contact, or if a visit is not scheduled after a minimum of three attempts using the participant's preferred mode of contact, or if a visit is not scheduled by the remaining two weeks of their

visit window, collaterals will be contacted in order to ask them questions regarding the participant's drinking. Participants will be instructed to provide names of individuals who see them often enough to know about their alcohol use and their current contact information. These individuals do not have to know about participants' HIV status, and that information will not be provided to them. Participants will be informed that collateral informants will be told that they are participating in a study being conducted at Fenway Health or Florida International University, and so they should choose people with whom they are comfortable sharing that information.

Measures

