Assessment focuses on six domains: (a) screening and background measures; (b) measures of alcohol use and problems, other substance use, and motivation to change; (c) measures of risky sexual behavior and ART adherence; (d) clinical assays and biomarker assessment; (e) measures of neurocognitive function; and (f) measures of treatment utilization. To reduce subject burden and potential assessment reactivity effects, assessments have been reduced to only those measures that are essential to study purposes. The interviews at baseline, 6 months, and 12 months should not exceed 120 minutes.

We will primarily use *measures that have already been approved as part of this protocol*. A description of each of the measures is provided below. We are not including copies of the measures that have been previously reviewed. Any additional measures will be submitted for approval prior to their implementation. Table 1 shows the schedule of assessments, indicating when each measure will be administered.

| Assessment: | Screening | Baseline - Session 1 | | 12-Month Follow-up |
|---|-----------|-------------------------|-----------|-----------------------|
| Measure | | 36351011 1 | F0110W-up | F0110W-up |
| Measure | | | | |
| Chart Review | Х | | | |
| Initial Screening | Х | | | |
| Medical Record Review | | Х | Х | Х |
| Alcohol Consequences Scale | | Х | | |
| Alcohol Contemplation Ladder | | Х | Х | Х |
| Alcohol-ART Interaction Beliefs and Behaviors | | Х | Х | Х |
| Alcohol and Drug Use History | | Х | | |
| Alcohol Withdrawal (SAWS/CIWA) | | Х | | |
| Antiretrovial Therapy (ART) | | Х | Х | Х |
| Adherence | | | | |
| Childhood Sexual Abuse | | Х | | |
| Conflict Tactics Scale (CTS) | | Х | | Х |
| Demographics | | Х | | |
| Depressive Symptoms (CES-D 10) | | Х | Х | Х |
| Drinking Motives | | Х | Х | Х |
| HIV History | | Х | Х | Х |
| HIV Stigma | | Х | Х | Х |
| Important People Assessment (IPA) | | Х | Х | Х |
| Internet and Communications Use | | Х | | |
| (Use of Technology) | | | | |
| LGBIS Internalized Homonegativity | | Х | | |
| Subscale | | | | |
| MINI 7.0 (DSM-V) | | Х | | |

Table 1. Schedule of Main Study Assessments

| Multiple Discrimination Scale | Х | | Х |
|------------------------------------|-------|------|------|
| Neurocognitive Assessment | Х | Х | Х |
| Quantity-Frequency Survey | Х | Х | Х |
| (Computer Assisted Self-Interview, | | | |
| CASI via Qualtrics) | | | |
| ReACH Website Access | | Х | Х |
| Serum collection | Х | Х | Х |

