IPA which has been widely used in studies addressing alcohol and other substance use behaviors (20).¹³ (13) The inclusion of this measure will allow us to better understand participant's social network characteristics of participants and whether they change over time as a function of the intervention. Childhood Sexual Abuse (CSA) (21): Numerous studies document a high prevalence of childhood sexual abuse (CSA) among HIV-positive gay and bisexual men, and has been associated with HIV risk and substance use behaviors (22, 23). We will administer an 8 item measure of CSA to better understand whether the intervention has a different impact on participants who have experienced CSA compared to those who have not

Collateral Reports. Collateral informants will be interviewed regarding the participant's drinking. These interviews will be confidential, and no information regarding the participant will be provided to the collateral. Collaterals will estimate the number of drinking days in the past month, the average number of drinks consumed per drinking day, and the number of heavy drinking days. They will indicate their level of confidence in their knowledge of the participant's drinking and only reports for which the collateral was at least "fairly confident" will be considered. The use of collaterals may increase honesty in reporting by participants and provides an index of the validity of self-reported drinking.

Measures of ART Adherence and Sexual Behavior

Timeline Followback (TLFB). The TLFB administered will be used to assess medication adherence and sexual risk behaviors as we have been doing in our current study. Due to the cognitive demands of completing a TLFB with alcohol, drug, sex, and adherence behavior, we will only go back 30 days from the interview for these measures. The TLFB has been shown to be a valid measure of adherence ^{14,15} and facilitates examination of alcohol-adherence associations on a daily basis ¹⁶⁻¹⁸. Participants will review each of the 30 days on the calendar, indicating the number of doses prescribed and taken each day. The dependent variable will be the percent of days with missed ART doses.

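### Does the narrow rule for contacting collateral informants leave self-reported drinking unchecked in a way that calls for a change to the plan?

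*Combined protocol and SAP*

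**What the plan says.** Collaterals appear in two places. Under Follow-up Assessments, the protocol invokes procedures already approved and states that "collateral informants will be interviewed to corroborate self-reports of drinking". Every participant is asked at intake to name up to two informants and may opt out. The operating rule comes next. If a visit is still unscheduled after at least three attempts, or when two weeks of the window remain, "collateral letters will be either mailed or emailed to informants depending on the contact information" the participant supplied. The letter tells the informant that staff have "permission to call them should there be a loss of contact with the participant". The letter also says, as a separate point, that the participant allows questions about his drinking. The sentence on calls begins "If a follow-up visit is not scheduled after a minimum of three attempts using the" participant's preferred contact route, repeats that clause, and ends by saying that "collaterals will be contacted in order to ask them questions regarding" his drinking.

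The Collateral Reports paragraph under Measures attaches no condition to the interviews. It lists what informants estimate, keeps only reports given with adequate confidence, and makes two claims: "The use of collaterals may increase honesty in reporting by participants", and the reports supply "provides an index of the validity of self-reported drinking"-type evidence. It adds no timing or sample. The Measures section says that "Table 1 shows the schedule of assessments, indicating when each measure will be administered"; as read, the table has no collateral row.

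The section on clinical assays and biomarkers lists phosphatidylethanol as a marker of recent alcohol use. Serum is scheduled at baseline, 6 and 12 months. The Statistical Analysis Plan covers two drinking outcomes, three secondary outcomes, a complete-data analysis and an imputed sensitivity analysis. It mentions neither collaterals nor phosphatidylethanol.

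**The concern.** Both primary outcomes are self-reported, and participants know which counselling they receive. Participants in the extended intervention (EI) have more contact with a counsellor: three sessions against two before the 6-month visit, and five against two before the 12-month visit. If more contact led men to report less drinking than they consumed, the EI effect would be exaggerated. An outside check on self-report would therefore be useful.

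The protocol appears to promise one, but its stated rule looks like a tracing procedure for men who are slipping out of follow-up. A man scheduled promptly never triggers it. A man never seen has no self-report to corroborate. That leaves a selected middle group, and agreement in that group says little about everyone else. A report could nevertheless cite the protocol and present those few pairs as validating the drinking data in general. Meanwhile, a biological marker of drinking is collected with no stated analysis.

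**Working it through.** The documents give no figure for collateral coverage or agreement, so there is nothing to reproduce. The check has four steps.

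**1. Contact rule against claims.** The corroboration and validity statements carry no condition; the stated trigger does. The letter sentence gives the trigger cleanly, so the garbled sentence on calls does not change the reading. The claim about honesty does not depend on the trigger, because all participants are asked to name informants at intake.

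**2. How many pairs the trigger could yield.** Pairs = 224 × share triggering × share of those later assessed (× share with a usable report, if counted). The 224 comes from the protocol; every share is assumed.

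| Triggering | Later assessed | Usable report | Pairs | Share of 224 |
|---|---|---|---|---|
| 0.10 | 0.50 | not applied | 224 × 0.10 × 0.50 = 11 | 5% |
| 0.30 | 0.80 | not applied | 224 × 0.30 × 0.80 = 54 | 24% |
| 0.10 | 0.25 | 0.50 | 224 × 0.10 × 0.25 × 0.50 = 3 | 1% |
| 0.30 | 0.50 | 0.80 | 224 × 0.30 × 0.50 × 0.80 = 27 | 12% |

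With 27 pairs and an assumed correlation of 0.6, the Fisher-z 95% interval is tanh(atanh(0.6) ± 1.96/√(26.9 − 3)), or 0.28 to 0.80. Routine contact, with 90% assessed and 50–80% usable reports (assumed), would give 101 to 161 pairs and intervals of 0.46–0.71 and 0.49–0.69. So if the trigger is the whole procedure and these rates are roughly right, the pairs are few as well as selected.

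**3. What a phosphatidylethanol comparison could show.** For one factor with n samples per level and correlation r with baseline, the 95% half-width in SD units is 1.96 × √((2/n)(1 − r²)). Full enrolment gives 112 per level (224/2); 90 and 100 are assumed, as is r.

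| n per level | r = 0 | r = 0.5 | r = 0.7 |
|---|---|---|---|
| 90 | 0.29 | 0.25 | 0.21 |
| 100 | 0.28 | 0.24 | 0.20 |
| 112 | 0.26 | 0.23 | 0.19 |

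Even with every sample present, modest differential under-reporting would fit inside the interval.

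**4. Effect on the planned results.** The primary model is log-linear in the mean. If men at both levels of a factor report the same fraction k of the true value, the ratio is kμ₁/kμ₀ = μ₁/μ₀, so equal proportional under-reporting cancels. Only a difference between levels biases the result. No collateral variable enters the primary model, the secondary models or the imputation as described. Rewording the collateral text therefore leaves every planned estimate, interval and test as it was.

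**The case for a change.** The best case for acting is that the text claims more than its procedure delivers, and correcting it is cheap. A few sentences would settle who is contacted, and one regression per assayed visit would put an existing marker to use. The other safeguards do not fill the same role: breath alcohol at the visit detects intoxication that day, and the computer-assisted interview is a second self-report. This stands as a comment on wording. A reader should not take pairs from the stated trigger as validating the whole sample.

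It does not stand as a defect that needs a remedy, for three reasons. First, the collateral procedure is partly incorporated by reference, and both general statements are unconditional. The triggered steps may be an addition to a routine interview described in the approved materials. The letter's separate permission to ask about drinking, which is not tied to lost contact, is consistent with that. Table 1 schedules participants' own visit assessments, so a missing row for third-party interviews is weak evidence. Second, any statement that the rule misses most of the sample rests on an assumed trigger rate. Third, phosphatidylethanol is one of many research assays and is nowhere offered as a check on self-report. The analysis plan also leaves out other secondary measures, such as the neurocognitive tests and the cytokine panel. Leaving out an exploratory marker is a choice of scope.

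**Conclusion.** No change is needed. The stated contact rule is narrower than the corroboration and validity claims, and the analysis plan names no external check on drinking. Both observations are correct. The first is loose wording in a document that relies on procedures it does not reproduce. The second is an analysis that could be added, not an error in those planned.

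The consequence for the planned results is nil, because none of them uses collateral reports. A phosphatidylethanol analysis would be supportive at best: with a half-width of about 0.19 to 0.29 SD, it would neither correct a bias in the primary result nor exclude a modest one. The main protections for the drinking outcomes lie elsewhere: follow-up interviewers who are not told the assignment, a calendar-cued 30-day interview, breath testing at assessments, assured confidentiality, and the computer-assisted interview meant to reduce under-reporting. The last EI session is at month 9, well before the 30-day recall at month 12.

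The conclusion would be different if a report presented collateral agreement as evidence for the whole sample without saying who was contacted; the documents plan no such report. The pair counts and half-widths rest on assumed rates and correlations and show only orders of magnitude.

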Aim 1: To test the hypothesis that MI compared to BA, ITM compared to no ITM, and EI compared to no EI, will result in significantly greater reductions in (1) the number of alcoholic drinks consumed and (2) the number of heavy drinking days at 6- and 12-month follow ups.

Aim 2: To test the effects of MI, ITM, and EI on engagement in unprotected anal intercourse, ART adherence and viral suppression.

Procedures

A number of procedures will mirror many of those previously approved. There will only be slight changes made to the explanation of the study in the study screener (see attached) with the primary change being the addition of text messaging, delivery of intervention by videoconferencing, and inclusion of at least minimal counseling for all participants. New consent forms are attached that reflect those changes. We will recruit heavy drinking HIV-infected MSM receiving primary care at Fenway Health or other health care facilities in the greater Boston, Massachusetts area and at Jackson Memorial Hospital Medical Center or other health care facilities in Miami, Florida. Participants will be recruited through fliers posted throughout the clinics and at HIV support groups and on community bulletin boards, as well as through proactive screening and recruitment during primary care visits at Fenway Health and at outside organizations that cater to HIV+ individuals. Screening procedures at outside organizations will only take place in either private rooms, hallways, or corners of rooms that are all out of the earshot of others. Study recruiters at Fenway Health will work closely with providers and CFAR Network of Integrated Clinical Systems (CNICS) staff to identify patients who would be eligible and interested in participating in this study. We will also advertise the study on social media websites like Facebook and Tumblr, online community bulletin boards like Craigslist, as well as on location-based, sex-seeking websites/apps (e.g. Grindr and SCRUFF) to further assist us with recruitment efforts. The online advertisement will include a link to a secure REDCap form that will request only the interested

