We aim to randomize 112 participants at each site using block randomization (16 per block) to ensure an equal number of participants in each of the treatment cells. Participants will receive their first session of MI/BA videocounseling immediately upon completion of the baseline interview. Research staff will share with the interventionist participant's information that is necessary for conducting the counseling session (drinking level, viral load, etc.) by uploading a report to a restricted and secure folder on the Brown server. Participants will be seated in a private room in the clinic that is equipped with a computer, speakers, a microphone, and a webcam. Research staff will instruct participants about how to use the videoconferencing tool on this computer. The videoconferencing software provides a secure, HIPAA compliant connection with the study's interventionists, who will be housed at Brown University. The software also allows secure sharing of the conferencing patient's medical information, which allows video counselors to share, present, and discuss this information, as relevant to the conversation. Each session conducted will be audio recorded for research and training purposes.

After the videoconference, participants in all conditions will be informed that they will be contacted by this same counselor by phone in 1 month, and that they will come back in for in-person interviews and questionnaires in 6 and 12 months. Those in the EI condition will be informed that they will receive an additional phone call from their counselor at 3 months, meet again with their counselor during their 6 month appointment, and then receive a final phone call at 9 months. Those in the ITM conditions will also be informed that they should expect to receive daily text messages beginning the next day. Those in the EI+ITM group will be told to expect the frequency of these messages to be reduced to weekly after the first 30 days.

Brief Intervention

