We will obtain complete demographic information on each participant who is eligible and will also assess depressive symptoms using the Center for Epidemiologic Studies – Depression scale [CES-D;²]. Depressive symptoms, which can sometimes result from excessive alcohol consumption, have been associated with poor ART adherence and are therefore important to assess as a covariate. The Treatment Services Review will assess use of major medical care outside of the health care facility where the participant normally receives care. Internet and Communication Use (use of technology) will be asked in order to learn what means of communication may be most effective in administering interventions in this population and whether there are potential barriers to the text messaging program. We will also ask participants how often they accessed the ReACH project website for information on alcohol use and HIV in the past 6 months. Experienced discrimination due to HIV status, race/ethnicity, and sexual orientation will be assessed with the Multiple Discrimination Scale³. Internalized homonegativity will be measured using a 5-item subscale from the Lesbian, Gay, and Bisexual Identity Subscale (Mohr & Fassinger, 2000).

Measures of Alcohol Use and Problems, Other Substance Use, and Motivation to Change

We will gather information about age of onset of alcohol use, period of heaviest drinking, most drinks consumed on a single day, and number of lifetime drug classes used. Current and past alcohol and substance use disorders (as well as screening for mania and psychosis) will be assessed at baseline using the MINI 7.0.1⁴. Urine Drug Screen. In addition to providing a breath sample for alcohol concentration analysis at each in-person assessment, participants also will provide a urine sample for testing for recent

drug use: PCP, ecstasy, barbiturates, methadone, oxycodone, benzodiazepines, methamphetamine, THC, opiates, and cocaine. Alcohol withdrawal symptoms will be assessed using the Clinical Institute Withdrawal Assessment for Alcohol, revised ¹.

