For primary outcomes—(a) drinks per week and (b) number of heavy drinking at 6- and 12months follow-ups—we fit marginalized zero-inflated negative binomial (MZI-NB) models to test the main and interactive effects of each of the three factors in the study design:

 $log \{E(Y)\} = \beta_0 + \beta_1 A + \beta_2 B + \beta_3 C + \beta_{12} AB + \beta_{23} BC + \beta_{13} AC + \beta_{123} ABC + \gamma X.$ (Eq1) with a similar logit model describing the excess zeros as in the traditional zero-inflation model. The terms *A*, *B*, and *C* in Eq1 are dummy variables for BI vs. MI, no ITM vs. ITM, and no EI vs. EI; and coded orthogonally so they can be evaluated concurrently with the three 2-way interactions and one 3-way interaction among these factors. The model parameters β_1 , β_2 and β_3 capture the main effects, and $\beta_{13}, \ldots, \beta_{123}$ capture the two- and three-way interaction effects. The models are adjusted for baseline covariates *X*, including the baseline value of the dependent variable, recruitment site, and indicators for interventionists. Following intention-to-treat principles, we conduct regression analyses on all participants who were randomized to an intervention condition regardless of the number of sessions of intervention they completed.

Secondary outcomes for this study are: (1) the number of days engaging in condomless sex with a non-steady partner in the past 30 days at 6 and 12 months, (2) percentage of the past 30 days taking all prescribed ART doses at 6 and 12 months, and (3) HIV viral suppression (i.e., <20 copies/ml) at 12 months. Due to limited variation in condomless sex and ART adherence outcomes, we dichotomize these, respectively, as: (a) 0 day vs \geq 1 day of condomless sex with non-steady partner and (b) \geq 95% ART adherent [i.e., perfect or near-perfect adherence] vs < 95% ART adherence. For secondary outcomes, logistic regression models, similar to the model above but replacing the left-hand side of Eq1 by *h*{*E*(*Y*)} with *h*(.) being the logit link function, were used to test the main and interactive effects of the three study factors.

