Missing data. We conducted our primary analyses using complete data. We also used re-ran analyses with imputed data as a sensitivity analysis. Imputation of missing data was carried out using the chained-equation method (R MICE package) assuming that data were missing at random. We maintained the longitudinal structure of the data and built imputation models that imputed missing values at 6 months only using baseline data and observed 6-month data, and imputed the missing values at the 12 months using baseline and imputed 6-month data and observed 12-month data. Imputations were iterated until the distribution of imputed values stabilized. Five complete datasets were created and used for regression analyses. The results were then pooled using Rubin's method^{56,57}.

References

- 2. Radloff LS. The CES-D scale: A self-report depression scale for research in the general population. *Applied Psychological Measurement*. 1977;1(Summer):385-401.

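### The protocol names depressive symptoms as a covariate because of their link to ART adherence, but the SAP does not list baseline CES-D in the adherence model; the cost is a little power, not bias

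*Combined protocol and SAP*

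**What the plan says.** Under Screening and Background Measures, the protocol explains why depression is measured: depressive symptoms "have been associated with poor ART adherence and are therefore important to assess as a covariate". Table 1 lists "Depressive Symptoms (CES-D 10)" at baseline, 6 months and 12 months. The first counselling session follows the baseline interview, so the baseline score precedes treatment.

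The Statistical Analysis Plan adjusts its primary models for baseline covariates X, "including the baseline value of the dependent variable, recruitment site, and indicators for interventionists". The secondary outcomes, ART adherence among them, use logistic models "similar to the model above but replacing the left-hand side of Eq1", so the same X carries over. Adherence at 6 and 12 months is analysed as at least 95% versus below 95%: "Due to limited variation in condomless sex and ART adherence outcomes, we dichotomize these". Depressive symptoms and the CES-D appear nowhere in the SAP, and no reason is given for leaving them out.

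**The concern.** The protocol justifies one measure as a covariate by its link to one outcome, and that measure is missing from the named adjustment set for that outcome. If the list of X is complete, the SAP departs from the protocol without saying so. If the word that opens the list means that other covariates may be added, X is not fully pre-specified, and CES-D could go in or out after the results are seen.

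What is at stake statistically is power for the factor effects on adherence. The outcome is binary, comes from a measure that the SAP says varies little, and is fitted with seven factor terms plus X in at most 224 men. A prognostic baseline variable that has already been collected is a cheap way to recover some power.

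**Working it through.** **Comparison of the texts.** The protocol names depressive symptoms as a covariate and collects the score at baseline. The SAP names three items for X and reuses X in the adherence model. CES-D is not one of the three.

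**The plan's own figures.** The documents give no alpha, power, effect size, adherence rate or dropout rate, so there is no stated figure to reproduce. Only the allocation can be checked. The plan reads "We aim to randomize 112 participants at each site using block randomization (16 per block)". That gives 112/16 = 7 full blocks per site, 224/8 = 28 men per cell and 224/2 = 112 per level of each factor.

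**Unadjusted power, for scale.** With 112 per level and a two-sided 0.05 test, power is 67% for 60% vs 75%, 77% for 70% vs 85%, and 46% for 75% vs 85%. These rates are assumed.

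**Effect of adding CES-D.** The SAP's logistic model was simulated with three orthogonally coded factors, all interactions, binary baseline adherence and site. Each simulated data set was fitted with and without baseline CES-D, with 8,000 data sets per scenario and a Wald test at two-sided 0.05. The inputs below are all assumptions:

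- marginal adherence 70%
- odds ratio 5 for baseline adherence
- conditional factor odds ratio 2.2 (1.0 for type I error)
- CES-D odds ratio 1.25, 1.5 or 2.0 per SD
- correlation of 0.2 in size between CES-D and the latent baseline-adherence score
- N = 224, or 192 (about 14% loss)

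Interventionist indicators were left out because their number is not given.

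| N | CES-D OR per SD | Power without | Power with | Gain (points) | Median SE of factor log-OR, without / with |
|---|---|---|---|---|---|
| 224 | 1.25 | 69.6% | 69.8% | 0.2 | 0.336 / 0.340 |
| 224 | 1.5 | 67.4% | 68.9% | 1.5 | 0.336 / 0.343 |
| 224 | 2.0 | 63.6% | 66.2% | 2.6 | 0.335 / 0.353 |
| 192 | 1.25 | 61.9% | 62.3% | 0.4 | 0.365 / 0.370 |
| 192 | 1.5 | 60.6% | 62.0% | 1.4 | 0.366 / 0.375 |
| 192 | 2.0 | 57.1% | 60.5% | 3.4 | 0.366 / 0.386 |

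One simulated power figure has a standard error of about √(0.67 × 0.33/8000) = 0.005, or half a point. Both models were fitted to the same data sets, so the differences are better determined than that, but the 0.2-point gain is effectively nil.

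**Why power rises while the SE also rises.** At N = 224 and CES-D odds ratio 2.0, the median factor log-OR moves from 0.769 to 0.837 and its SE from 0.335 to 0.353. The ratio goes from 0.769/0.335 = 2.30 to 0.837/0.353 = 2.37. The estimate moves away from zero by proportionally more than the SE grows.

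**Type I error.** At N = 224 the rejection rate with no factor effect is 0.053 to 0.057 without CES-D and 0.053 to 0.058 with it.

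**The case against.** The protocol sentence is a reason for measuring depression. It calls the measure important and reports an association; it does not require adjustment or specify a model. The SAP's list of X is not stated to be exhaustive, so the documents show only that CES-D is not named. A short X of baseline outcome, site and interventionist is a legitimate choice, and baseline adherence is likely to carry most of the prognostic information. Randomisation protects the factor tests from bias with or without CES-D. All of this stands. It limits the point to a small one, but it does not explain why the covariate named in the protocol is absent.

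Three stronger readings are tempting, and the documents do not support them.

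- **That the estimates lose precision.** In a logistic model a prognostic covariate does not shrink the SE of the conditional log-OR. Here it rises by about 1% to 5%. The gain is in power only.
- **That the omission costs 4% to 15% of the sample.** With a log-OR b of 0.35 to 0.70 per SD, b²/(b² + 3.29) is 3.6% to 13%, and 1/(1 − R²) − 1 then gives about 4% to 15%, or 8 to 33 of 224 men. That is a linear-model formula applied to latent logistic variance. It ignores baseline adherence, already in X, and it takes all 224 men as the base. The eligibility criteria set conditions for men on ART but do not require ART, so the adherence denominator may be smaller.
- **That the whole of Aim 2 is affected.** The aim is "To test the effects of MI, ITM, and EI on engagement in unprotected anal intercourse, ART adherence and viral suppression". The protocol ties depression to adherence alone among these. Extending the point to condomless sex or viral suppression would be the reader's own inference.

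**Conclusion.** The point holds for the ART adherence models only. The protocol names depressive symptoms as a covariate and collects the CES-D 10 at baseline, and the SAP does not name it in X. The factor tests stay valid. The power forgone is about 0 to 3 percentage points: 0.2 to 2.6 at N = 224 and 0.4 to 3.4 at N = 192. These figures depend entirely on the assumed CES-D odds ratio of 1.25 to 2.0 per SD, 70% adherence, a factor odds ratio of 2.2 and a strong baseline-adherence effect. With a weak CES-D effect the gain vanishes. This is a cheap improvement and a reconciliation of two texts, not a flaw that threatens the conclusions.

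**What to change.** Add the baseline CES-D 10 score, as a continuous term, to X in the logistic models for ART adherence at 6 and 12 months, and state that the list of X is complete. Use the baseline score only; the 6- and 12-month scores are measured after randomisation and may be affected by the interventions.

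The SAP is partly written in the past tense. If outcomes have already been analysed, keep the current model and report the CES-D-adjusted one beside it as a labelled sensitivity analysis, so that the covariate choice cannot look driven by results.

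The cost is one SAP line and one degree of freedom in a model whose outcome varies little. Because the primary analysis uses complete data, any man without a baseline CES-D would also drop out of the adjusted model, and with a gain this small, even modest missingness could cancel it. The imputation text does not settle this: it "imputed missing values at 6 months only using baseline data and observed 6-month data" without listing the variables, and it serves only the sensitivity analysis. Count the missing baseline scores before making the change.
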